5.3 Definitions

5.3.1 Adverse Events

Adverse event is any untoward medical occurrence in a clinical investigation by a subject who has been administered a product or medical device; the event need not necessarily have a causal relationship with the study procedures. Adverse events include the following:

- All suspected procedure-related adverse events.
- Apparently unrelated illnesses, including the worsening of a preexisting illness (see fifth bullet, below, regarding preexisting conditions).

- Injury or accidents. Note that if a medical condition is known to have caused the injury or accident (e.g., a fall secondary to dizziness), the medical condition (dizziness) and the accident (fall) should be reported as 2 separate adverse events. If an accident results in a subsequent adverse event (e.g., hip fracture secondary to the fall), both the accident and the subsequent event should be recorded in the adverse event CRF.
- Abnormalities in physiological testing or physical examination findings that require clinical intervention or further investigation unless they are associated with an already reported adverse event. A test or an examination that is repeated to check a possible abnormality does not constitute an adverse event.
- Preexisting condition (i.e., a disorder present before the adverse event reporting period started and noted on the pretreatment medical history/physical examination form) should not be reported as an adverse event unless the condition worsens or episodes increase in frequency during the adverse event reporting period.

5.3.2 Serious and Unexpected Adverse Events

A serious adverse event is any untoward medical occurrence that:

- Results in death;
- Is life-threatening (i.e., puts the patient or clinical investigation subject at immediate risk of death; but not an event that, had it been more severe, might have created a risk of death);
- Requires inpatient hospitalization or prolongation of existing hospitalization;
- Results in persistent or significant disability/incapacity;
- Results in congenital anomaly/birth defect.

Medical and scientific judgment should be exercised in determining whether an event is an important medical event. An important medical event may not be immediately life threatening and/or result in death or hospitalization. However, if it is determined that the event may jeopardize the patient and may require intervention to prevent one of the other outcomes listed in the definition above, the important medical event should be reported as serious.

An unexpected adverse event is any adverse drug experience, the specificity or severity of which is not consistent with the current investigator brochure; or, if an investigator brochure is not required or available, the specificity or severity of which is not consistent with the risk information described in the general investigational plan or elsewhere in the study documents. In this case, “expected” does not include events that are anticipated based on pharmacological properties.

5.4 Adverse Event Follow-up

The investigator will document all directly observed adverse events and all adverse events spontaneously reported by the trial subject. In addition, each trial subject will be questioned about adverse events by phone at 24 hours post imaging. The question asked will be “Since your MRI examination, have you had any health problems?”

6 Statistical Plan

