We have initiated a proof of concept study under IND 104,917 and with local IRB approval (Evaluation of Regional Ventilation in Normal Subjects and Subjects with Airway and Lung Disorders Using 19F Magnetic Resonance Imaging of Inert Perfluorinated Gases mixed with Oxygen (PFP): A Phase 1 Study). We have consented 44 subjects minus one withdrawal, screened 43 subjects in the study with the characteristics described in Table 1 and scanned 30 subjects (reasons for non scanning of subjects: 1 voluntary withdrawal prior to any study participation, 5 body habitus (too obese), 4 screen fails, 4 MRI contraindications).

Disease Status	Number of Subjects Screened (F/M)
Normal	13 (5/8)
COPD	11(7/4)
COPD, Emphysema	4 (1/3)
COPD Emphysema, Asthma, Small Airway Disease	1(1/0)
COPD Asthma, Small Airway Disease	1 (1/0)
Asthma	2 (2/0)
Asthma, small airway Disease	2 (2/0)
Cystic Fibrosis	5 (4/1)* all with lung transplant
Lung Transplant	2 (1/1)
Small Airway Disease	1 (1/0)
Unknown Etiology	1 (0/1)
Total	43 (25/18)

Table 1: Disease profiles of screened subjects in the phase 1 proof of concept study

2 Trial Objectives

The proposed study will determine regional qualitative and quantitative lung function information in the context of the clinical trajectory of COPD defined by the cross sectional cohort components. Due to the long time-frame of this disease we are using a modified case control design that allows a cross-sectional evaluation of the proposed measures in aims 1-2 to identify putative markers that could later be tested as prognostic factors in longitudinal studies. In the case of these PFx/oxygen mixtures, the availability of multi-liter quantities allows for wash-in/wash-out image acquisition and analysis allowing direct measures of gas trapping in a manner not easily achieved with any existing modality.

3 Trial Design

The central hypothesis and current observation is that PFx gases used as contrast agents provide functional images of the lung airways including important regional ventilation information such as ventilation defect severity and gas trapping. We will test the central hypothesis and accomplish the overall objective by addressing the following specific aims:

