3.3 Duration

3.3.1 Screening (V0)

1. Obtaining Informed Consent from each subject
2. History and Physical exam. The history will focus on onset of symptoms, co-morbidities, and smoking/occupational/environmental history. Also included:
 - a. An assessment of patterns of exacerbations (mild = use of oral antibiotics and/or steroids for an acute change in respiratory status; moderate = hospital admission for a change in respiratory status; severe = requirement for mechanical ventilation for a change in respiratory status).
 - b. A measurement of the body mass index (BMI).
 - c. A medication history (oral steroids, chronic bronchodilator use, oxygen use) with an emphasis on whether adherence was adequate.
 - d. Assessment of gastro-esophageal reflux disease (10)
 - e. Epworth Sleepiness Scale as a marker of sleep disordered breathing

- f. Estimate of daily physical activity (25)
- 3. Pulmonary function tests will include spirometry, plethysmographic lung volumes, and corrected carbon monoxide diffusing capacity (DLCO). All procedures will be done in accordance with ATS/ERS standards (3) (15) (17).
- 4. High resolution computerized scans of the chest (HRCT). Emphysema scores will be calculated per COPD Gene protocol (7). We will also explore novel approaches to quantifying airway structures (5) (16)
- 5. A six-minute walk test with monitoring of pulse oximetry and heart rate will be conducted in accordance with ATS standards (1)
- 6. Vital Signs will be measured and recorded (temperature, heart rate, blood pressure and respiratory rate)
- 7. Pulse oximetry will be measured and recorded.
- 8. Weight and height will be recorded.
- 9. Quality of Life (QOL) will be assessed using the St George self-administered instrument
- 10. A serum pregnancy test will also be performed in women with child bearing potential.

MRI will be collected at the study visit 1 after the screening visit. Where possible the screening visit (V0) and MRI visit (V1) will be accomplished on the same day for the convenience of the subject. In all cases, the MRI will be followed-up immediately following the MRI procedure for any adverse events. Finally, all subjects will be contacted 24 hours post-MRI by phone for follow-up regarding any adverse events.

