3.3.3 Twenty-four Hour Follow-up

Twenty-four hours post V1 (and subsequent imaging visits) the subjects will be contacted by phone and questioned regarding any post MRI adverse events. (Refer to Table 2 for the scheduled of events.)

Table 2: Scheduled of Events

Protocol Activities	Screening (V0)	Study Visit (V1)	Follow Up (24 hours by phone)
Informed Consent	X		
General Medical History	X		
Physical Exam	X		
HRCT ¹	X		
Weight and Height	X		
Concomitant Medication	X		
Pregnancy Test (serum and urine) ²	X		
Quality of Life Assessment	X		
MRI Screening Form	X	X	
Vital Signs Assessment	X	X	
Pulse oximetry	X	X	
Six Minute Walk Test	X		
Thermally Polarized Gas MRI			X
Pulmonary Function Test	X		
Adverse Event Assessment		X	X
¹ depending on scheduling, the HRCT will be performed at screening (V0) or between screening (V0) – study visit (V1)			
² Females of child-bearing potential who had a blood pregnancy tests performed, will have a urine pregnancy test if blood test was given 48 or more hours earlier			

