3.5 Data Identification

According to ICH and FDA guidance, the following data will be considered source and will be recorded directly into each subject's CRFs.

- Screening (V0)
 - Informed Consent date
 - General Medical History
 - Physical Exam
 - Weight/Height
 - Concomitant Medications
 - Quality of Life Assessment
 - Vital Signs
 - Pulse Oximetry
 - 6 Minutes Walk
 - PFT First section
- Study Visit (V1)
 - Vital Signs (pre and post imaging)
 - Pulse Oximetry (pre and post imaging)
 - For Women of child bearing potential
 - Date of the results of the pregnancy test
 - Adverse Events (post imaging)
- 24hr Follow up phone call
 - Adverse Event
 - Follow-up

The following data will be considered source but will not be recorded directly into each subject's CRFs. This data will likely be found in the subject's research folder (paper) and/or electric medical record.

- Informed Consent
- For Women of child bearing potential
 - Result of pregnancy test
- MRI screening Form
- HRCT reading
- PFT Testing results

The CRFs, the MR/HRCT images and PFT testing results will serve as source documents for this study.

4 Selection of Subjects and Withdrawal/Discontinuation

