5.2 Adverse Event Reporting

Any adverse event will be reported to the IRB and DSMC, and any other regulatory agents, and serious adverse events will be reported within 24 hours. An annual progress report (or more frequently, if requested) will be submitted to the IRB, DSMC and any other regulatory agents.

Significant morbidity and mortality are anticipated in these study subjects due to the nature of the disease. Deaths, exacerbations of COPD, and hospitalizations for any cause are outcome measures of the trial and will not be reported as adverse events. These outcomes will be monitored by the DSMC. In accordance with policies of the NIH, other serious events, including severe injuries and new diagnosis of potentially fatal or disabling medical conditions will be reported as serious adverse events of the study to the local IRB, the DSMC, and the NIH. The clinical investigator(s) will terminate the study immediately if the occurrence of serious adverse events that suggests unacceptable risk to the health of the subjects. All observed or volunteered adverse events, regardless of suspected causal relationship to the study procedure(s), will be recorded on the adverse events page(s) of the CRF's or worksheets. Events involving adverse experiences occurring during the study procedure(s) will be recorded.

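### Active adverse event inquiry starts only after the MRI, so events from the screening procedures are under-ascertained, most clearly in subjects who never reach MRI

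*Combined protocol and SAP*

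**What the plan says.** Four places in the protocol set when adverse events are asked about.

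- Section 3.3.1 ties the on-site check to the scan: "the MRI will be followed-up immediately following the MRI procedure for any adverse events". It ties the phone call to the scan as well: "all subjects will be contacted 24 hours post-MRI by phone for follow-up regarding any adverse events".
- Section 3.3.3, Table 2: the row "Adverse Event Assessment" carries two marks, which by position are V1 and the 24-hour call. There is none at V0.
- Section 3.5: the V1 list of data entered directly in the CRF contains "Adverse Events (post imaging"). The V0 list has no adverse event item.
- Section 5.4: "each trial subject will be questioned about adverse events by phone at 24 hours post imaging", and the script is "Since your MRI examination, have you had any health problems".

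Section 5.2 is broader: "Events involving adverse experiences occurring during the study procedure(s) will be recorded". Sections 5.2 and 5.4 also require observed and volunteered events to be recorded, without limiting this to a visit. Section 5.3.1 counts suspected procedure-related events as adverse events.

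**The concern.** V0 is not free of procedures. Section 3.3.1 places spirometry and the other lung function tests, a six-minute walk, HRCT and a serum pregnancy test there. Section 1.3.1 lists bronchospasm from spirometry, and pain, hematoma and dizziness from blood sampling, as study risks. These are short-term events that a simple question could bring out, but no scheduled question covers the time when they would occur.

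At stake is the completeness of the safety record for the study procedures. Events noticed only by the subject, or arising after the subject has left V0, enter the record only if the subject volunteers them. There is also no same-day symptom question before the gas, which would help in deciding whether a complaint after the MRI is new.

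**Working it through.** **1. When active inquiry takes place**

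| Source | At V0 | At V1 before the gas | At V1 after MRI | 24-hour call |
|---|---|---|---|---|
| 3.3.1 | none | none | yes | yes |
| Table 2 | none | not distinguished | V1 marked | yes |
| 3.5 CRF lists | none | none | yes | yes |
| 5.4 script | – | – | no wording given | since the MRI |

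Column positions in the extracted table could have shifted, but sections 3.3.1, 3.5 and 5.4 lead to the same conclusion without it.

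**2. Who falls outside it**

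- *Subjects who stop before MRI.* Both scheduled contacts are defined relative to the scan, so these subjects have neither. This can happen late: under section 3.3.2, MRI safety rescreening and the repeat pregnancy test may take place at V1, after all V0 procedures are complete.
- *Subjects with V0 and V1 on different days.* Section 3.3.1 combines the visits only when that can be arranged and gives no maximum gap. Footnote 1 of Table 2 allows the HRCT in between. Staff cannot observe a hematoma or bronchospasm that develops at home.

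**3. The only figure on subjects not reaching MRI** (earlier phase 1 study, section 1.6, Preliminary Studies)

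- Consented: 44. Reasons for not being scanned: 1 + 5 + 4 + 4 = 14.
- 44 − 14 = 30, which reproduces the stated "scanned 30 subjects".
- The rows of Table 1 sum to 43 screened. Screened but not scanned: 5 + 4 + 4 = 13, and 43 − 30 = 13.
- 13/43 = 30.2%; exact (Clopper-Pearson) 95% CI 17.2% to 46.1%.

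**4. Illustration for this study** (assumption: the same loss applies to the planned 250)

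- If 250 counts enrolled subjects: 250 × 0.302 ≈ 76 without a scheduled inquiry (250 × 0.172 ≈ 43 to 250 × 0.461 ≈ 115).
- If 250 counts scanned subjects: 250/(1 − 0.302) − 250 ≈ 108 further subjects screened without one (52 to 214 at the interval limits).
- The interval reflects sampling error only. Section 1.6 does not say how many of the 13 had a risk-bearing procedure. If only the 4 labelled screen fails had, the share would be 4/43 = 9.3%, or about 23 of 250 enrolled.

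These figures count subjects not asked, not events missed. The documents give no event rates for the V0 procedures.

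**The case against.** The case for leaving the plan alone has substance, and several stronger readings that a reader might infer do not hold.

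- *That V0 events are excluded.* They are not. Sections 5.2 and 5.4 record observed and volunteered events at any visit, and V0 procedures are attended by staff, so acute dizziness or bronchospasm would normally be seen. This stands. What remains is that section 5.4 itself adds active questioning to passive capture, but only for the time after the MRI.
- *That nobody is asked about the interval between V0 and V1.* This is unproven. The script belongs to the phone call. The wording of the V1 check is not given and could reach back in subjects who attend V1.
- *That there is no symptom record before the MRI.* The documents contradict this. V0 has history, physical examination, medication history and the St George questionnaire, and V1 has vital signs and oximetry before imaging. Only a same-day symptom question is missing.
- *That the CT risk belongs on the list.* Section 1.3.4 describes cancer later in life, which no question at these visits could detect.
- *That three in ten subjects here will go unasked.* The earlier study included asthma, cystic fibrosis and transplant subjects, and exposure of the 13 to V0 procedures is unknown.

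It can also be said that the risks are minor: section 1.3.1 describes them so, and the only blood test named at V0 is the pregnancy test in women of childbearing potential. That is fair, and it limits the importance of the point. Finally, section 5.3.1 defines an adverse event in someone already given a product or device, and the gas is given only at V1. On that reading V0 events might not count at all. But the same section includes suspected procedure-related events and refers to a reporting period whose start it never states, so the definition is ambiguous and does not settle the matter.

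**Conclusion.** The point holds in a limited form. Scheduled, active inquiry begins only after the MRI, while the protocol's own definition takes in procedure-related events and its risk list names short-term risks of tests done at V0. The result is under-ascertainment, firmest in subjects who stop before MRI and for delayed events when the two visits are on different days.

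Its size in events cannot be derived from the documents. The 30% (17% to 46%) is an upper-end illustration of how many screened subjects might have no scheduled inquiry. It assumes that the earlier study's loss carries over and that all those lost had undergone a risk-bearing procedure. No aim, sample size or planned analysis is affected. This is a minor, inexpensive improvement to safety ascertainment.

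**What to change.** 1. Mark the adverse event row at V0 in Table 2 and add an adverse event item to the V0 CRF list in section 3.5.
2. At V1, before the gas is given, ask about health problems since the screening visit. This covers the interval between visits and provides a same-day symptom baseline.
3. For subjects who do not proceed to MRI, ask after their last study procedure. A phone call on the model of the 24-hour call would also reach delayed events, which a question at the end of V0 would miss.
4. In section 5.3.1, state when the adverse event reporting period starts, and reconcile the definition's reference to subjects given a product or device with its inclusion of procedure-related events.

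The 24-hour question can stay as it is once the pre-MRI question exists. Widening it to the time since the last contact would add nothing, because that contact is the check straight after the MRI.

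The cost is a short amendment, a table mark and CRF fields, about a minute of staff time per subject, and somewhat more minor events to record and to report to the IRB and DSMC.

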6.1 Statistical Methods and Subject Population for Analysis

We have three main methods to employ to characterize of clinical phenotypes using MR Imaging bases features.

One method is to estimate with reasonable precision the mean and standard deviation ventilation parameters from 19F gas imaging. So with 250 (5 groups) subjects we should be able using a t-test (or ANOVA) to detect a variation in defect volume of approximately 6% in the smallest sample (N = 26/group, GOLD III/IV) (alpha 0.05 and 90% power) and 5% in the reference groups (N=40/group). [Statmate Ver 2, GraphPad Software (La Jolla, Ca)].

Further, we wish to evaluate the diagnostic/prognostic ability of the MRI parameters to provide distinction among current ‘phenotypes’ and perhaps extend better discrimination with the MRI parameters from study aims. We will also use statistical modeling for this project to correlate the features obtained from the gas-probe MR imaging-based measures with one or more of the clinical assessment measures recorded in Aim 1.2, to better characterize disease phenotypes and identify the most promising prognostic indicators.

In a similar context, a recent study has shown such promise for certain CT imaging-based features (7). Thus, if the role of MR imaging-based measures can be established in a similar fashion then, associated with a link f , is some MR-defined variable Z which can define a biomarker, risk factor or phenotype R , resulting in the general linkage statement of $R \leftarrow f \rightarrow \text{GOLD+MRI}$. The makeup of this biomarker would contain information obtained from one or more measures Aims 1, 1.1 and 2 as well as other clinical status information X (as codified in the GOLD score or more generally some combination of the demographic, physiological and past history information, (Aim 1.2). This biomarker would then provide a more rapid and efficient means for deciding treatment strategies. We will examine the diagnostic/phenotyping ability of the MR imaging-based features (Aims 1 and 2) in terms of their ability to predict existing clinical phenotypes (GOLD) characterized and other clinical features (Aim 1.2). For this purpose, we will divide the predictors into two categories: a) clinical assessments features ($X_{a1}, X_{a2}, \dots, X_{ak}$), obtained from existing clinical, physiologic, and HRCT imaging, measured under Specific Aims 1.1 and 1.2; b) features obtained from MR imaging ($X_{b1}, X_{b2}, \dots, X_{bl}$), identified under Aims 1 and 2. A generalized linear model of the form [1] will be fitted using the method of maximum likelihood:

$$g(Y_t) = \beta_{a0} + \beta_{a1}X_{a1} + \dots + \beta_{ak}X_{ak} + \epsilon \quad [1]$$

The predictability of this model will be calculated using the Akaike Information Criterion (AIC) statistic (2), which balances the quality of fit (likelihood) against model complexity (8). Selection of the optimal subset of predictors will be achieved via a search over predictor space to identify the subset that maximizes the AIC statistic.

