1.5 Trial Design

An open label study in 250 subjects over five years. We are planning 130 subjects with COPD (varies stages of GOLD I-IV) and 120 normal subjects (non-smokers, ex smokers and current smokers with normal PFT's).

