3.1 Primary Study Aims/Secondary Aims

Aim 1: Determine quantitative measures of lung ventilation performance in terms of direct measures of gas trapping measured during washout of the perfluorinated gas mixture.

Sub-aim 1.1: Compare gas trapping from aim 1 with air trapping by HRCT using conventional analysis procedures.

Sub-aim 1.2: We will accomplish this aim (as well as Aim 2) in a well-characterized cohort of subjects with COPD and subjects with normal global pulmonary function tests (non-, ex- and current smokers). This cohort will provide the basis for the cross sectional evaluation of the imaging markers in all aims with respect to disease severity (e.g. GOLD status) and risk factors (e.g. smoking)

Aim 2: Determine ventilation defect severity by comparing regional gas signal during wash-in of the perfluorinated gas mixture to steady state in the same cohort.

The outcomes of the work proposed in the aims is expected to demonstrate a novel quantitative approach for ventilation defect and gas trapping evaluation of regional lung function in humans that would be easily deployed for multi-center studies. It should also provide a set of biomarkers that could better inform evaluation of new treatments.

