4.1 Inclusion/Exclusion Criteria for Subjects with COPD

Inclusion criteria

Subjects must meet all of the following inclusion criteria to be eligible for enrollment into the

trial

1. Outpatients of either gender, age > 18.
2. Willing and able to give informed consent and adhere to visit/protocol schedules.
(Consent must be given before any study procedures are performed.)
3. Women of childbearing potential must have a negative serum pregnancy test. This will be confirmed before participation in this investigational protocol.
4. Clinical diagnosis of COPD confirmed by Spirometry demonstrating FEV1/FVC <0.70.

Exclusion criteria

Subjects presenting with any of the following will not be included in the trial:

1. Abuse of alcohol or illicit substances.
2. Medical conditions, which, in the opinion of the investigator, will significantly affect five-year survival.
3. Medical or psychological conditions which, in the opinion of the investigator, might create undue risk to the subject or interfere with the subject's ability to comply with the protocol requirements.
4. Conditions that will prohibit MRI scanning (metal in eye, claustrophobia, inability to lie supine, renal insufficiency with eGFR < 60 mL/min/1.73 m²)

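### Section 6.1 names only a t-test or ANOVA for comparing MRI measures between groups, so nothing planned gives an age-adjusted group difference in this unmatched case-control cohort

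*Combined protocol and SAP*

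**What the plan says.** Sub-aim 1.2 (section 3.1) makes the cohort the basis for a "cross sectional evaluation of the imaging markers in all aims with respect to disease severity (e.g. GOLD status) and risk factors (e.g. smoking"). Section 2 describes the design: "we are using a modified case control design that allows a cross-sectional evaluation of the proposed measures". Section 1.5 sets the numbers: "We are planning 130 subjects with COPD (varies stages of GOLD I-IV) and 120 normal subjects".

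For a difference in an MRI measure between groups, section 6.1 names one method, in its detectability statement: "we should be able using a t-test (or ANOVA) to detect a variation in defect volume of approximately 6% in the smallest sample". The accompanying figures are ("N = 26/group, GOLD III/IV) (alpha 0.05 and 90% power) and 5% in the reference groups (N=40/group"). No covariate is mentioned.

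Sections 4.1 and 4.2 admit COPD and normal subjects on the same criterion: "Outpatients of either gender, age > 18". No matching, stratification or restriction by age or sex is described.

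Section 6.1 also plans a generalized linear model. It judges the MRI features "in terms of their ability to predict existing clinical phenotypes (GOLD) characterized and other clinical features (Aim 1.2"). Clinical status may enter it as the GOLD score or as "some combination of the demographic, physiological and past history information".

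**The concern.** Group is not randomised here, and neither the design nor the named test controls age or sex. If COPD and reference subjects differ in age, and defect volume or gas trapping varies with age, a t-test or ANOVA cannot separate the two influences.

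The study is exploratory. It seeks candidate markers to be tested later as prognostic factors in longitudinal studies. What is at stake is carrying forward a marker that mainly tracks age. For a fixed imbalance, the chance of a false positive grows with sample size, so a pooled COPD v normal contrast is the most exposed.

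**Working it through.** **Inputs from the plan (sections 6.1 and 1.5).** Alpha 0.05; power 90%; 6% at 26 per group; 5% at 40 per group; 130 COPD and 120 normal subjects.

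**Assumptions.** The test is two-sided, % means percentage points, and SDs are equal across groups. The plan gives no SD, age gap, age slope or within-group age SD. It does not name a 26 v 40 or a 130 v 120 test; these pairings are chosen here from its group sizes.

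**1. The plan's own figures.** The exact t-test has 90% power at a difference of 0.917 SD with 26 per group and 0.734 SD with 40 per group. The implied SDs are:
- 6 / 0.917 = 6.54 points
- 5 / 0.734 = 6.81 points

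The two figures agree after rounding, and they describe an unadjusted comparison.

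**2. Error rate of the unadjusted test with no disease effect.** Let the age-driven shift be b = slope × age gap. The rejection rate comes from the noncentral t with noncentrality b / (SD × √(1/n1 + 1/n2)). The standard error is 1.65-1.72 points at 26 v 40 and 0.83-0.86 at 130 v 120.

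| Assumed shift | Example | 26 v 40 | 130 v 120 |
|---|---|---|---|
| 0.5 | 0.1/year × 5 years | 5.9-6.0% | 8.9-9.2% |
| 1 | 0.1/year × 10 years | 8.9-9.2% | 21.1-22.5% |
| 2 | 0.1/year × 20 years | 20.9-22.3% | 63.7-67.2% |

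The error rate reaches 10% at a shift of 1.09-1.14 points (26 v 40) or 0.54-0.56 points (130 v 120). At 0.25 points it is only 5-6%.

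**3. Sex.** A 2-point sex difference with a 20-percentage-point imbalance in the proportion female gives a shift of 2 × 0.20 = 0.4 points. The rates are then 5.6-5.7% and 7.5-7.7%. An extreme case of 3 × 0.30 = 0.9 points gives 8.1-8.4% and 18.0-19.1%.

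**4. Effect of adjustment.** In simulation (10,000 runs per setting, 1- and 2-point shifts), a linear model with group, age and sex rejected in 4.8-5.3% of runs. That is expected, since the fitted model matches the one that generated the data.

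**5. Price of adjustment.** The variance of the group difference is multiplied by 1 + p(1−p) × gap² / (age SD)², where p is the share of subjects in one group. At 26 v 40, p(1−p) = 0.239. A 10-year gap with age SD 10 gives 1.24; a 20-year gap gives 1.96. With age SD 12 the factors are 1.17 and 1.66.

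| Age gap | Power for 6 points, 26 v 40 | Detectable difference at 90% power, 130 v 120 |
|---|---|---|
| Unadjusted | 93-95% | 2.7-2.8 points |
| 10 years | 87-91% | 2.9-3.1 points |
| 20 years | 69-79% | 3.5-4.0 points |

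**The case against.** The strongest reply is that the generalized linear model already covers this. A model of GOLD on MRI features and age tests the same null hypothesis: that the MRI measure is unrelated to group once age is known. It would largely expose an age-only marker. In simulation with such a marker (slope 0.1 per year, SD 6.7, age SD 10), best-subset AIC kept age in 99-100% of runs at 130 v 120 for gaps of 5 to 20 years. At 26 v 40 it kept age in 99-100% for gaps of 10 to 20 years and 71% for a 5-year gap.

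This holds only if age is a candidate predictor. The list of clinical predictors does not name it; demographic information appears only as a possible ingredient of the biomarker. Equation [1] as printed has no MRI term. No form of that model gives an adjusted difference in defect volume or gas trapping. The sentence in section 6.1 about correlating MRI features with clinical measures does not say which side is the outcome, and it names no covariate.

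Other objections stand as limits on the finding. The t-test appears only in a detectability statement, not in a full analysis specification, although no other between-group method for an MRI measure is given. The shifts are assumed, and the contrasts were chosen for illustration. The study is exploratory. Adjustment costs precision.

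**Conclusion.** The concern holds and should be acted on. The plan names no method that would show whether a group difference in an MRI measure persists after allowing for age or sex, and its design does not balance them.

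The consequence is conditional. A shift of 0.5 points hardly matters at 26 v 40, whereas 2 points would make a pooled comparison significant in about two-thirds of studies with no disease effect. These sizes rest on the back-solved SD and the assumed shifts. The documents do not show which case applies. Age is the main issue; sex matters less unless both the imbalance and the sex difference are large.

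**What to change.** In section 6.1, state that each MRI measure will be compared between groups by a linear model with group, age and sex, and that the adjusted difference with its 95% confidence interval will be reported beside the unadjusted one. Handle smoking in separate, stated contrasts, because Sub-aim 1.2 studies it as a risk factor. Say that the quoted 90% power refers to the unadjusted comparison. Show the age distribution by group so that readers can judge overlap.

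Two optional additions: keep age and sex in the AIC-selected model whatever the search finds, and frequency-match on age band and sex any reference subjects still to be recruited.

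The main change is wording and needs no new data, since age and sex are known from eligibility. The real cost is the loss of precision shown above: appreciable in the small groups if the age gap is wide, but modest in the pooled contrast, whose detectable difference stays below the plan's 5 to 6 points. Where the age ranges barely overlap, the adjusted estimate depends on the model, and the report should say so.
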